**Figure 4. Bar chart for R0 and R9 output [PP Population]**

**Figure 5. Bar chart for R2, R5, and R7 output [PP Population]**

**Sponsor:** ThermiGen, LLC.  
**Protocol Number:** Thermi\_0005  
**Protocol:** *An Open-Label, Single-Center, Single-Treatment, Safety and Effectiveness Evaluation of Percutaneous Radiofrequency in Achieving Submental Lift*  
**Version:** Protocol Rev. A; SAP Rev. B

Table 10									
Overall Treatment Emergent Adverse Events Summary [1] [2]									
Safety Population									
		After Treatment Prior to Day 30		After Day 30, up to Day 60		After Day 60, up to Day 90		After Day 90, up to day 180	
		N=XXX		N=XXX		N=XXX		N=XXX	
		# Events	Subjects w/Event % (n/N)	# Events	Subjects w/Event % (n/N)	# Events	Subjects w/Event % (n/N)	# Events	Subjects w/Event % (n/N)
All Adverse Events		XX	XX.X (X/XX)	XX	XX.X (X/XX)	XX	XX.X (X/XX)	XX	XX.X (X/XX)
Device Related		XX	XX.X (X/XX)	XX	XX.X (X/XX)	XX	XX.X (X/XX)	XX	XX.X (X/XX)
Serious Adverse Events		XX	XX.X (X/XX)	XX	XX.X (X/XX)	XX	XX.X (X/XX)	XX	XX.X (X/XX)
Device Related		XX	XX.X (X/XX)	XX	XX.X (X/XX)	XX	XX.X (X/XX)	XX	XX.X (X/XX)

[1] Events reported as adjudicated or by site if not adjudicated

[2] Denominators of time points are subjects past the visit window or with an event

Listing 10						
Summary of Adverse Events						
Subject ID	Adverse Event Number	SOC (Preferred Term)	Days Post Procedure	Any Adverse Event	Any Serious Adverse Event	Event Related to Study Treatment
XX-XXX	XX	XX	XX	XX	XX	XX

**Sponsor:** ThermiGen, LLC.  
**Protocol Number:** Thermi\_0005  
**Protocol:** *An Open-Label, Single-Center, Single-Treatment, Safety and Effectiveness Evaluation of Percutaneous Radiofrequency in Achieving Submental Lift*  
**Version:** Protocol Rev. A; SAP Rev. B

Table 11 Overall Treatment Emergent Adverse Events Summary by System Organ Class and Preferred Term [1] [2] Safety Population										
	After Treatment Prior to Day 30 N=XX		After Day 30, up to Day 60 N=XX		After Day 60, up to Day 90 N=XX		After Day 90, up to day 180 N=XX		Total N=XX	
	# Events	Subjects w/Event % (n/N)	# Events	Subjects w/Event % (n/N)	# Events	Subjects w/Event % (n/N)	# Events	Subjects w/Event % (n/N)	# Events	Subjects w/Event % (n/N)
All Adverse Events	XX	XX.X (X/XX)	XX	XX.X (X/XX)	XX	XX.X (X/XX)	XX	XX.X (X/XX)	XX	XX.X (X/XX)
SOC 1	XX	XX.X (X/XX)	XX	XX.X (X/XX)	XX	XX.X (X/XX)	XX	XX.X (X/XX)	XX	XX.X (X/XX)
PT 1.1	XX	XX.X (X/XX)	XX	XX.X (X/XX)	XX	XX.X (X/XX)	XX	XX.X (X/XX)	XX	XX.X (X/XX)
PT 1.2	XX	XX.X (X/XX)	XX	XX.X (X/XX)	XX	XX.X (X/XX)	XX	XX.X (X/XX)	XX	XX.X (X/XX)
SOC 2	XX	XX.X (X/XX)	XX	XX.X (X/XX)	XX	XX.X (X/XX)	XX	XX.X (X/XX)	XX	XX.X (X/XX)
PT 2.1	XX	XX.X (X/XX)	XX	XX.X (X/XX)	XX	XX.X (X/XX)	XX	XX.X (X/XX)	XX	XX.X (X/XX)
PT 2.2	XX	XX.X (X/XX)	XX	XX.X (X/XX)	XX	XX.X (X/XX)	XX	XX.X (X/XX)	XX	XX.X (X/XX)
each System Organ Class	XX	XX.X (X/XX)	XX	XX.X (X/XX)	XX	XX.X (X/XX)	XX	XX.X (X/XX)	XX	XX.X (X/XX)
each Preferred Term	XX	XX.X (X/XX)	XX	XX.X (X/XX)	XX	XX.X (X/XX)	XX	XX.X (X/XX)	XX	XX.X (X/XX)

[1] Events reported as adjudicated or by site if not adjudicated

[2] Denominators of time points are subjects past the visit window or with an event

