## 5 SAMPLE SIZE

The null and alternative hypotheses are:

$$\begin{aligned}
 H_0: \pi &\leq 0.45 \text{ (or 45\%)} \text{ vs.} \\
 H_a: \pi &> 0.45
 \end{aligned}$$

where  $\pi$  is the true proportion of subjects with at least 20 mm^2 lift. Under the assumptions that

1.  $\pi = 0.70$  (or 70%) for subjects not prematurely withdrawing from the study; and
2. The dropout rate is 12.5% and all dropouts will be considered as non-responders

a sample of size 70 enrolled subjects provides approximately 85% power to reject the null hypothesis in favor of the alternative at a one-sided  $\alpha=0.05$ .

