### 6.3 SAFETY

The safety population of this study will include all enrolled subjects who received at least one treatment.

For clarification purposes of the analysis populations described in sections 6.1 – 6.3, the following table from section 8.6.2 of the clinical protocol has been included here for reference (Table 1).

**Table 1.** Subject Status Classification

Classification	Criteria
Screen Failure	Signs the ICD but does not meet entry criteria or withdraws prior to Visit 2.
Enrolled	Signs the ICD and met all inclusion/exclusion criteria
Treated	Signs the ICD and successfully completes V2
Discontinued/Withdrawal	Signed the ICD but does not successfully complete any visits
Completed	Signs the ICD and successfully completes all study visits

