## 11 SAFETY ANALYSIS

All adverse events (AEs) will be coded using the standardized Medical Dictionary for Regulatory Activities (MedDRA) central coding dictionary, version 19.1 or greater. All analyses described below will be performed on the Safety Population.

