### 11.2 ALL ADVERSE EVENTS

Summaries of incidence rates and relationship to the investigational device of individual treatment emergent AEs (TEAE) by System Organ Class (SOC) and Preferred Term (PT) will be prepared. A treatment emergent adverse event is defined as an event that started or worsened in severity at or after the first attempt at treatment. Because a subject may experience more than one TEAE, summaries will provide both the number of subjects and the number of events within a reporting period. Percentages provided will be the percent of subjects in the Safety Population experiencing one or more adverse events.

A listing of all adverse events will include the subject number, AE number, days since procedure, the AE SOC and PT, the severity of AE, whether or not the AE is classified as serious (SAE), the relationship of the AE to the investigational device or procedure, the action taken, the outcome, and the adjudication status.

AEs will be recorded for all enrolled subjects to time of withdrawal, and reported in a table for all Safety subjects.

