### 11.4 SERIOUS ADVERSE EVENTS (SAE)

Summaries of incidence rates and relationship to the investigational device/procedure of individual serious TEAEs SAEs by SOC and PT will be prepared. Summaries will provide both the number of subjects and the number of events within a reporting period. Percentages provided will be the percent of subjects experiencing one or more serious adverse events. A data listing of SAEs will also be provided, displaying details of the event(s) captured on the CRF.

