Intention to Treat Population (ITT)	XX.X (X/XX)
Per Protocol Population (PPP)	XX.X (X/XX)
Safety Population (SAF)	XX.X (X/XX)
Note: Percentages are based on "All Enrolled"	

Listing 1				
Analysis Populations				
Subject ID	Enrolled	ITT	PP	SAF
XX-XXX	Yes/No	Yes/No	Yes/No	Yes/No

**Sponsor:** ThermiGen, LLC.  
**Protocol Number:** Thermi\_0005  
**Protocol:** *An Open-Label, Single-Center, Single-Treatment, Safety and Effectiveness Evaluation of Percutaneous Radiofrequency in Achieving Submental Lift*  
**Version:** Protocol Rev. A; SAP Rev. B

[figure not shown]
Table 2 Subject Accountability ITT Population				
Visit	Eligible N	Missed % (n/N)	Complete % (n/N)	Early Exit % (n/N)
Screening	XXX			
Procedure	XX	XX.X (X/XX)	XX.X (X/XX)	XX.X (X/XX)
Day 30	XX	XX.X (X/XX)	XX.X (X/XX)	XX.X (X/XX)
Day 60	XX	XX.X (X/XX)	XX.X (X/XX)	XX.X (X/XX)
Day 90	XX	XX.X (X/XX)	XX.X (X/XX)	XX.X (X/XX)
Day 180	XX	XX.X (X/XX)	XX.X (X/XX)	XX.X (X/XX)

Note: Percentages are based on the number of subjects in the ITT Population.

Listing 2 Subject Accountability								
Subject ID	Screening Date	Procedure Date	30 Day Visit	60 Day Visit	90 Day Visit	180 Day Visit	Study Exit	Exit Reason
XX-XXX	Date9.	Date9.	Date9.	Date9.	Date9.	Date9.	Date9.	

**Sponsor:** ThermoGen, LLC.  
**Protocol Number:** Thermo\_0005  
**Protocol:** *An Open-Label, Single-Center, Single-Treatment, Safety and Effectiveness Evaluation of Percutaneous Radiofrequency in Achieving Submental Lift*  
**Version:** Protocol Rev. A; SAP Rev. B

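### Footnote [2] on adverse-event Tables 10 to 15 lets having an event decide who enters the interval denominator, conflicts with the Safety Population base in SAP 11 and 11.2, and can inflate interval percentages

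*SAP*

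**What the plan says.** **Text of the SAP.** Section 11 sets the population for all safety work: "All analyses described below will be performed on the Safety Population". Section 6.3 defines it: "The safety population of this study will include all enrolled subjects who received at least one treatment". Membership depends on treatment only, not on length of follow-up or on events. Section 11.2 gives the percentage base: "Percentages provided will be the percent of subjects in the Safety Population experiencing one or more adverse events". The same section says that "summaries will provide both the number of subjects and the number of events within a reporting period", but defines no separate denominator for a reporting period. Section 11.4 is less explicit ("Percentages provided will be the percent of subjects experiencing one or more serious adverse events"), and section 11.5 is worded in the same way for device- and procedure-related events.

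**Shells.** Tables 10 to 15 are all titled as Safety Population tables and split follow-up into four intervals with cut points at Days 30, 60, 90 and 180. All six carry footnote [2]: "Denominators of time points are subjects past the visit window or with an event".

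**Table 2 (Subject Accountability).** Each visit row has an Eligible N and columns for missed, complete and early exit. The note below reads "Note: Percentages are based on the number of subjects in the ITT Population". Protocol 8.4 and Appendix 1 limit Visit 4 (Day 60) to the first 30 subjects enrolled.

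**The concern.** Take two treated subjects who leave on the same day, before a window closes. If being past the window requires continued follow-up, the footnote counts the one who had an event and drops the one who did not. Selecting the denominator on the outcome is a fault in itself, whatever its size in this trial. It also means that the table title and SAP 11.2 call for one percentage and the footnote for another, so a programmer cannot follow both.

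The footnote leaves two further matters open. It does not say whether the event must fall in that interval, be of the type in that row, or have occurred at any time. Nor does it say how the Day 60 window applies to the 40 of 70 subjects who have no Day 60 visit.

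Safety is a stated aim of the study (Protocol 11.1), and these tables are its main output. Table 2 has a related but separate denominator fault: subjects never scheduled for Day 60 are counted in the base of the Day 60 percentages.

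**Working it through.** **Inputs from the documents.** SAP 5 plans 70 subjects ("a sample of size 70 enrolled subjects provides approximately 85% power to reject the null hypothesis") with 12.5% dropout: 0.125 × 70 = 8.75, taken as 9. Visit 4 applies to 30 subjects (Protocol 8.4).

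**Inputs assumed.** All 70 are treated, so the Safety Population is 70. The event counts and the timing of exits are illustrative, because the documents give none.

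**The plan's own safety figure.** The plan states no adverse-event percentage to reproduce. Its one safety figure is the rule of three in Protocol 11.2 (at least 60 subjects, 5% frequency, 95% confidence). It checks: 3/60 = 5.0%, and 1 − 0.95^60 = 95.4%. The denominator question does not affect it.

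**Footnote against Safety Population.** Suppose D subjects leave before the window closes and k of them have an event in the interval. Then

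- footnote denominator = (70 − D) + k
- Safety Population denominator = 70
- ratio of the two percentages = 70 / (70 − D + k)

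| With event | D | k | Footnote | Safety Population |
|---|---|---|---|---|
| 7 | 0 | 0 | 7/70 = 10.0% | 10.0% |
| 7 | 2 | 0 | 7/68 = 10.3% | 10.0% |
| 7 | 5 | 0 | 7/65 = 10.8% | 10.0% |
| 7 | 9 | 0 | 7/61 = 11.5% | 10.0% |
| 14 | 9 | 0 | 14/61 = 23.0% | 20.0% |
| 14 | 9 | 2 | 14/63 = 22.2% | 20.0% |
| 14 | 9 | 9 | 14/70 = 20.0% | 20.0% |
| 28 | 9 | 0 | 28/61 = 45.9% | 40.0% |

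Against the full Safety Population, the footnote percentage is equal or higher, never lower. At the planned dropout the ratio is at most 70/61 = 1.15. In these cases the excess runs from 0 to 5.9 points.

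**Day 60 column.** Suppose only the 30 Visit 4 subjects can be past the Day 60 window. Take 7 subjects with an event, 3 among the 30 and 4 among the other 40, and no exits. The footnote denominator is 30 + 4 = 34, giving 7/34 = 20.6% against 7/70 = 10.0%.

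**Interim report.** SAP 3.1.2 plans a report before database lock, when many subjects may not have reached the later windows. Suppose 30 subjects are past Day 180, 4 of them with an event, and 3 subjects still in follow-up have an event. The footnote gives 7/33 = 21.2%; among the fully followed it is 4/30 = 13.3%. The SAP does not say which shells the interim report uses.

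**Table 2.** If all 30 scheduled subjects attend Day 60, the note gives 30/70 = 42.9%. On the row's own Eligible N it is 30/30 = 100%.

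**The case against.** The strongest reply is that the footnote never mentions early exit. Being past the visit window may simply mean that enough time has elapsed since treatment. Final analyses run only after the last subject's Day 180 visit (SAP 3.2). On that reading nearly every treated subject is past every window by then, the denominator is essentially the Safety Population, and any distortion is confined mainly to the interim report. This reading is possible and the documents do not exclude it. It does not rescue the wording: the footnote does not say so, and its second limb still admits subjects because they had an event.

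A reader might infer that every interval percentage is biased upward. The documents do not support that. Inflation needs at least one event in the cell and at least one event-free subject not past the window. The direction also depends on the comparator. If the second limb covers anyone who ever had an event, 9 exits with an earlier event stay in a later interval's denominator: 7/70 = 10.0% against 7/61 = 11.5% among those still followed, which is downward.

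A reader might also infer that the denominator changes between organ-class and preferred-term rows. The shells show one N per column, so that is inference.

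The conflict with the text is clearest for Tables 10 and 11. For Tables 12 to 15 it rests on the general statement in SAP 11, on SAP 11.3 and on the table titles. The footnote speaks of time points and need not govern the Total columns. Safety has no formal test, cells print n/N, and each table has a listing, so rates can be recalculated. These points limit the consequence but leave the rule wrong as written.

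On Table 2, a careful reader would see an Eligible N of 30 and no missed visits beside 42.9%. That softens the misreading, but the printed percentage still has the wrong base.

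**Conclusion.** The point holds as a minor one. Footnote [2] makes the interval denominator depend on the outcome, is ambiguous, and conflicts with the Safety Population base in SAP 11 and 11.2. It can inflate interval percentages; it need not.

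The bound of about 1.15 assumes 70 treated, the whole planned dropout falling before one window closes, and no event among those who leave. The effect is zero without event-free subjects outside the window, and largely disappears from the final tables if the window is read as elapsed time. The bound does not cover the interim report or a Day 60 column limited to 30 subjects. The documents settle neither case.

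The Table 2 fault needs no assumption about events or exits; the 42.9% takes an ITT population of 70. The primary endpoint and the sample size are unaffected.

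**What to change.** **Tables 10 to 15.** Replace footnote [2] with a rule that does not refer to events. For each interval, use Safety subjects in follow-up at its start, with or without an event, including those who have no Day 60 visit. For the Total column, use all Safety subjects.

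**SAP 11.2, 11.4 and 11.5.** Add a matching sentence. This is necessary because a denominator of subjects still in follow-up also departs from the present 11.2 text in later intervals. If the sentence in 11.2 is worded to cover all interval tables, it also reaches Table 15 (section 11.3).

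**Table 2.** Base each row's percentages on that row's Eligible N, which is 30 at Day 60. This also fits SAP 7.2, which speaks of scheduled assessments, and SAP 11.1, which already treats Day 60 as a sample of 30.

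**Effect on the worked example.** If the 9 event-free subjects leave during the interval, all 70 were in follow-up at its start and the result is 14/70 = 20.0%. If they left before it began, it is 14/61 = 23.0%, because none of them could contribute an event. In both cases follow-up, not the outcome, sets the denominator.

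**Cost.** One repeated footnote, one table note and a sentence in three SAP sections. No new data and no change to conduct. The downside is that interval percentages may change slightly from those under the shell rule.

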**NOTE: This SOC and PT structure to be carried forward to tables**

Listing 11 Summary of Adverse Events by SOC and PT						
Subject ID	Adverse Event Number	SOC (Preferred Term)	Days Post Procedure	Any Adverse Event	Any Serious Adverse Event	Event Related to Study Treatment
XX-XXX	XX	XX	XX	XX	XX	XX

**Sponsor:** ThermiGen, LLC.  
**Protocol Number:** Thermi\_0005  
**Protocol:** *An Open-Label, Single-Center, Single-Treatment, Safety and Effectiveness Evaluation of Percutaneous Radiofrequency in Achieving Submental Lift*  
**Version:** Protocol Rev. A; SAP Rev. B

Table 12									
Overall Treatment Emergent Serious Adverse Events Summary by System Organ Class and Preferred Term [1] [2]									
Safety Population									
		After Treatment Prior to Day 30		After Day 30, up to Day 60		After Day 60, up to Day 90		After Day 90, up to day 180	
		N=XX	N=XX	N=XX	N=XX	N=XX	N=XX	Total	
		# Events	Subjects w/Event % (n/N)	# Events	Subjects w/Event % (n/N)	# Events	Subjects w/Event % (n/N)	# Events	Subjects w/Event % (n/N)
All Serious Adverse Events		XX	XX.X (X/XX)	XX	XX.X (X/XX)	XX	XX.X (X/XX)	XX	XX.X (X/XX)
each System Organ Class		XX	XX.X (X/XX)	XX	XX.X (X/XX)	XX	XX.X (X/XX)	XX	XX.X (X/XX)
each Preferred Term		XX	XX.X (X/XX)	XX	XX.X (X/XX)	XX	XX.X (X/XX)	XX	XX.X (X/XX)

[1] Events reported as adjudicated or by site if not adjudicated

[2] Denominators of time points are subjects past the visit window or with an event

Listing 12						
Summary of Serious Adverse Events by SOC and PT						
Subject ID	Adverse Event Number	SOC (Preferred Term)	Days Post Procedure	Any Adverse Event	Any Serious Adverse Event	Event Related to Study Treatment
XX-XXX	XX	XX	XX	XX	XX	XX

**Sponsor:** ThermiGen, LLC.  
**Protocol Number:** Thermi\_0005  
**Protocol:** *An Open-Label, Single-Center, Single-Treatment, Safety and Effectiveness Evaluation of Percutaneous Radiofrequency in Achieving Submental Lift*  
**Version:** Protocol Rev. A; SAP Rev. B

Table 13										
Device-Related Treatment Emergent Adverse Events Summary by System Organ Class and Preferred Term [1] [2]										
Safety Population										
	After Treatment Prior to Day 30		After Day 30, up to Day 60		After Day 60, up to Day 90		After Day 90, up to day 180		Total	
	N=XX		N=XX		N=XX		N=XX		N=XX	
	# Events	Subjects w/Event % (n/N)	# Events	Subjects w/Event % (n/N)	# Events	Subjects w/Event % (n/N)	# Events	Subjects w/Event % (n/N)	# Events	Subjects w/Event % (n/N)
All Device-related AEs	XX	XX.X (X/XX)	XX	XX.X (X/XX)	XX	XX.X (X/XX)	XX	XX.X (X/XX)	XX	XX.X (X/XX)
each System Organ Class	XX	XX.X (X/XX)	XX	XX.X (X/XX)	XX	XX.X (X/XX)	XX	XX.X (X/XX)	XX	XX.X (X/XX)
each Preferred Term	XX	XX.X (X/XX)	XX	XX.X (X/XX)	XX	XX.X (X/XX)	XX	XX.X (X/XX)	XX	XX.X (X/XX)

[1] Events reported as adjudicated or by site if not adjudicated

[2] Denominators of time points are subjects past the visit window or with an event

Listing 13						
Summary of Adverse Events Related to Study Treatment						
Subject ID	Adverse Event Number	SOC (Preferred Term)	Days Post Procedure	Any Adverse Event	Any Serious Adverse Event	Event Related to Study Treatment
XX-XXX	XX	XX	XX	XX	XX	XX

**Sponsor:** ThermiGen, LLC.  
**Protocol Number:** Thermi\_0005  
**Protocol:** *An Open-Label, Single-Center, Single-Treatment, Safety and Effectiveness Evaluation of Percutaneous Radiofrequency in Achieving Submental Lift*  
**Version:** Protocol Rev. A; SAP Rev. B

Table 14 Device-Related Treatment Emergent Serious Adverse Events Summary by System Organ Class and Preferred Term [1] [2]										
Safety Population										
	After Treatment Prior to Day 30		After Day 30, up to Day 60		After Day 60, up to Day 90		After Day 90, up to day 180		Total	
	N=XX	N=XX	N=XX	N=XX	N=XX	N=XX	N=XX	N=XX		
	# Events	Subjects w/Event % (n/N)	# Events	Subjects w/Event % (n/N)	# Events	Subjects w/Event % (n/N)	# Events	Subjects w/Event % (n/N)	# Events	Subjects w/Event % (n/N)
All Device-related, Serious AEs	XX	XX.X (X/XX)	XX	XX.X (X/XX)	XX	XX.X (X/XX)	XX	XX.X (X/XX)	XX	XX.X (X/XX)
each System Organ Class	XX	XX.X (X/XX)	XX	XX.X (X/XX)	XX	XX.X (X/XX)	XX	XX.X (X/XX)	XX	XX.X (X/XX)
each Preferred Term	XX	XX.X (X/XX)	XX	XX.X (X/XX)	XX	XX.X (X/XX)	XX	XX.X (X/XX)	XX	XX.X (X/XX)

[1] Events reported as adjudicated or by site if not adjudicated

[2] Denominators of time points are subjects past the visit window or with an event

Listing 14 Summary of Serious Adverse Events Related to Study Treatment						
Subject ID	Adverse Event Number	SOC (Preferred Term)	Days Post Procedure	Any Adverse Event	Any Serious Adverse Event	Event Related to Study Treatment
XX-XXX	XX	XX	XX	XX	XX	XX

**Sponsor:** ThermiGen, LLC.  
**Protocol Number:** Thermi\_0005  
**Protocol:** *An Open-Label, Single-Center, Single-Treatment, Safety and Effectiveness Evaluation of Percutaneous Radiofrequency in Achieving Submental Lift*  
**Version:** Protocol Rev. A; SAP Rev. B

Table 15									
Treatment Emergent Adverse Events Leading to Withdrawal Summary by System Organ Class and Preferred Term[1] [2]									
Safety Population									
		After Treatment Prior to Day 30		After Day 30, up to Day 60		After Day 60, up to Day 90		After Day 90, up to day 180	
		N=XX		N=XX		N=XX		N=XX	
		# Events	Subjects w/Event % (n/N)	# Events	Subjects w/Event % (n/N)	# Events	Subjects w/Event % (n/N)	# Events	Subjects w/Event % (n/N)
All Adverse Events		XX	XX.X (X/XX)	XX	XX.X (X/XX)	XX	XX.X (X/XX)	XX	XX.X (X/XX)
each System Organ Class		XX	XX.X (X/XX)	XX	XX.X (X/XX)	XX	XX.X (X/XX)	XX	XX.X (X/XX)
each Preferred Term		XX	XX.X (X/XX)	XX	XX.X (X/XX)	XX	XX.X (X/XX)	XX	XX.X (X/XX)

[1] Events reported as adjudicated or by site if not adjudicated

[2] Denominators of time points are subjects past the visit window or with an event

Listing 15								
Summary of Adverse Events Leading to Withdrawal								
Subject ID	Adverse Event Number	SOC (Preferred Term)	Days Post Procedure	Any Adverse Event	Any Serious Adverse Event	Event Related to Study Treatment	Event Led to Subject Withdrawal	Comments
XX-XXX	XX	XX	XX	XX	XX	XX	XX	XX

**Sponsor:** ThermiGen, LLC.  
**Protocol Number:** Thermi\_0005  
**Protocol:** *An Open-Label, Single-Center, Single-Treatment, Safety and Effectiveness Evaluation of Percutaneous Radiofrequency in Achieving Submental Lift*  
**Version:** Protocol Rev. A; SAP Rev. B

Table 16 Numerical Rating Scale (NRS) Safety Population				
	Day 30	Day 60 [1]	Day 90	Day 180
	N=XX	N=XX	N=XX	N=XX
NRS				
Mean ± SD (N)	XX.X ± XX.X (XX)			
Median (Min, Max)	XX.X (XX.X, XX.X)	XX.X (XX.X, XX.X)	XX.X (XX.X, XX.X)	XX.X (XX.X, XX.X)
Change in NRS from Day 30				
Mean ± SD (N)	N/A	XX.X ± XX.X (XX)	XX.X ± XX.X (XX)	XX.X ± XX.X (XX)
Median (Min, Max)	N/A	XX.X (XX.X, XX.X)	XX.X (XX.X, XX.X)	XX.X (XX.X, XX.X)
Change in NRS from Day 90				
Mean ± SD (N)	N/A	N/A	N/A	XX.X ± XX.X (XX)
Median (Min, Max)	N/A	N/A	N/A	XX.X (XX.X, XX.X)

[1] 30 subjects in sequential order of enrollment chosen for 60 day visit.

Listing 16 Numerical Rating Scale (NRS)				
Subject ID	Day 30	Day 60	Day 90	Day 180
XX-XXX	XX	XX	XX	XX

**Sponsor:** ThermiGen, LLC.  
**Protocol Number:** Thermi\_0005  
**Protocol:** *An Open-Label, Single-Center, Single-Treatment, Safety and Effectiveness Evaluation of Percutaneous Radiofrequency in Achieving Submental Lift*  
**Version:** Protocol Rev. A; SAP Rev. B

Table 17 Protocol Deviations ITT Population				
Category	Reason	Time Period	N=XX	
			# Deviations	Number of Subjects with Deviation % (n/N)
		Enrollment	XX	XX.X (X/XX)
		Baseline	XX	XX.X (X/XX)
		Treatment	XX	XX.X (X/XX)
		30 day follow-up	XX	XX.X (X/XX)
		90 day follow-up	XX	XX.X (X/XX)
		180 day follow-up	XX	XX.X (X/XX)
			XX	XX.X (X/XX)
			XX	XX.X (X/XX)
			XX	XX.X (X/XX)
			XX	XX.X (X/XX)
			XX	XX.X (X/XX)

Listing 17 Protocol Deviations			
Subject ID	Category	Reason	Time Period
XX-XXX	XX	XX	XX

**Sponsor:** ThermoGen, LLC.  
**Protocol Number:** Thermo\_0005  
**Protocol:** *An Open-Label, Single-Center, Single-Treatment, Safety and Effectiveness Evaluation of Percutaneous Radiofrequency in Achieving Submental Lift*  
**Version:** Protocol Rev. A; SAP Rev. B

Table 18 Study Exit ITT Population	
	N=XX
Study status, % (n/N)	
Complete	XX.X (X/XX)
Early exit	XX.X (X/XX)
Time to early exit (days)	
Mean ± SD (N)	XX.X ± XX.X (XX)
Median (Min, Max)	XX.X (XX.X, XX.X)
Reason for early exit, % (n/N)	
Subject withdrew consent [1]	XX.X (X/XX)
Study terminated prematurely by sponsor	XX.X (X/XX)
Subject non-compliance	XX.X (X/XX)
Adverse Event/Serious Adverse Event [2]	XX.X (X/XX)
Other [3]	XX.X (X/XX)

Note: Percentages are based on the number of subjects in the ITT Population.

[1] See supporting listing for reasons for consent withdrawal

[2] See supporting listing for adverse events/serious adverse events

[3] See supporting listing for other reason for early exit

Listing 18 Study Exit				
Subject ID	Study Status	Time to Exit (Days)	Reason for Early Exit	Comments
XX-XXX	XX	XX	XX	XX
